3.3 Rationale for dose/regimen, route of administration and duration of treatment

The dose regimen for ofatumumab for this study is a *loading dose regimen* of 20 mg at Day 1, Day 7 and Day 14, followed by a *maintenance dose regimen* of 20 mg administered every 4 weeks starting at Week 4. Patients randomized to placebo in the Core will receive the ofatumumab 20 mg *loading dose regimen* during the extension at Week 24, 25 and 26, followed by a *maintenance dose regimen* of 20 mg administered every 4 weeks starting at Week 28.

The dose selection relies on the clinical hypothesis that the depletion of B-cells in lymphatic tissues is key for efficacy (as measured by MRI and relapses), and that the depletion of brain parenchymal and meningeal B-cells may be an additional factor for the mode of action; blood B-cell count is an imperfect, epiphenomenal measure of tissue status. This hypothesis suggests that, in order to attain the desired efficacy, 2 conditions should be met:

- A loading regimen with high enough initial PK for lymphatic depletion, and
- A continued maintenance dose that would keep B-cell depletion levels below desired threshold.

The Phase 2 study of ofatumumab sc (3 mg, 30 mg, 60 mg every 12 (q12) weeks, 60 mg every 4 (q4) weeks) in relapsing MS patients (Study OMS112831) provided important information on regarding the relationship between peripheral B-cell depletion and efficacy as measured by MRI Gd-enhancing brain lesions. Clear dose-response relationship was detected using a quasi-Poisson regression model that related new Gd-enhancing lesion volumes, baseline lesion number and treatment group. The dose-response was fully explained by the extent of the CD19+ cell count drop. The model indicates that lower CD19+ cells levels lead to better control of lesion volumes and, subsequently, high level of depletion of CD19+ cells (e.g. ≤ 8 cells/ μ L) should be maintained throughout the treatment course in order to ensure desired efficacy.

PK/PD modeling on the Phase 2 data of Study OMS112831 suggested that a single dose of ofatumumab 20 mg sc is insufficient to reduce B-cell levels to ≤ 8 cells/ μ L. A loading

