2.1.1 General definitions

Study drug/treatment refers to the investigational drug Ofatumumab and placebo.

“Date of Cut-off 2” is expected as the date the last patient completes all assessments at Week 48 visit. If the last patient discontinues from the study prior to Week 48 visit, “date of Cut-off 2” is the last patient's last visit.

Date of first administration of study drug/treatment, or first date of study drug/treatment, is defined depending on the analysis purposes.

- For Cut-off 1 analysis and Cut-off 2 and final *efficacy* analysis, it refers to the date when the first dose of randomized treatment is administered.
- For Cut-off 2 and final *safety* analysis, it refers to the date when the first dose of ofatumumab is administered.

Date of last administration of study drug/treatment, or last date of study drug/treatment is defined by analysis time point.

- For Cut-off 1 analysis, it refers to the date when the last dose of randomized treatment is administered up to Week 24 visit.
- For Cut-off 2 analysis, it refers to the date when the last dose of treatment is administered up to the date of Cut-off 2.
- For final analysis, it refers to the date when the last dose of treatment is administered up to EOS visit.

Study day is defined as: if after first date of study drug, then (Study Day) = (Date) – (first date of study drug) +1; if before first date of study drug, then (Study Day) = (Date) – (first date of study drug); Study Day 1 is defined as the date of the first administration of study drug; there is no Study Day 0.

Duration of an event is calculated as (event end date) – (event start date) +1.

1 month is counted as 30 days unless otherwise specified.

Baseline is defined for each cut-off analysis.

- For Cut-off 1 analysis, and Cut-off 2 and final *efficacy* analysis, baseline is defined as the last non-missing result before or on the first date of study drug.
- For Cut-off 2 and final *safety* analysis, definition of baseline depends on each patient's treatment course in the study
 - For a patient continuously having ofatumumab across Core and Extension parts, baseline is defined as the last non-missing result before or on the first date of study drug.
 - For a patient switching the treatment from placebo to ofatumumab when entering the Extension part, baseline is defined as the dose date of ofatumumab at Week 24. *For analysis on vital signs*, the baseline is defined as *the pre-dose measurement* at Week 24.

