On-treatment period is defined as the one between the first date of study drug and 30 days after the last date of study drug. The on-treatment definition applies to efficacy analyses only.

“Safety cut-off” is defined as 100 days after the last dosing date of the study drug.

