2.4 Treatments (study treatment, rescue medication, concomitant therapies, compliance)

2.4.1 Study treatment / compliance

Analyses detailed in this section will be performed for Cut-off 1 analysis, Cut-off 2 and final analysis.

For the core part and the extension part, duration of exposure to study drug is defined as (last dose date) – (first dose date) + 31 – sum[(j+1)-th injection date – j-th injection date - 31], where j and j+1 refer to consecutive injections with injection dates more than 31 days apart (as patients are scheduled to take the subcutaneous injections every 28+/- 3 days).

Duration of exposure to study drug of core part and extension part will be summarized by treatment with number and percentage of patients and by duration category (i.e., >= 1 week, >= 2 weeks, >= 3 weeks, >= 4 weeks, >= 8 weeks, >= 12 weeks, >= 24 weeks, >= 36 weeks, >= 48 weeks, >= 60 weeks, >= 72 weeks, until end of the study). The number of patient years of exposure is calculated as (the sum of the number of days of exposure for all

patients in the group)/365.25 and will be summarized for each treatment arm, and by stratification factor Japan vs non-Japan.

Time at risk is the censoring time used for estimating exposure adjusted incidence rate of SAEs or AEs in patients who did not experience the event of interest. For patients who have experienced the event of interest, the actual date of the SAE, or AE onset will be used. Time at risk corresponds to the time window used for adverse event reporting and can serve as a denominator to certain safety analyses (e.g. in exposure-adjusted incidence rates).

Table 2-10 includes definition of time at risk for AE and SAE for Cut-off 1 analysis. It will determine the “end date of the Core part” when all randomized patients completed their assessment during the Core part.

Table 2-10 Time at risk for AE and SAE: Cut-off 1 analysis

Category	For those who completed Week 24 visit	For those discontinued the study prior to Week 24 visit
Time at risk for AE	Number of days in the study from first date of study drug to Week 24 visit date	Number of days in the study from first date of study drug to the earlier date of the following: - Safety cut-off - “End date of the Core part”*
Time at risk for SAE		Number of days in the study from first date of study drug to “end date of the Core part”

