*: “End date of the Core part” will denote the date when all randomized patients complete Week 24 visit or discontinue study drug prior to Week 24 visit. This date is going to be declared by the study team, but not derived from any data.

Table 2-11 includes definition of time at risk for AE and SAE for Cut-off 2 and final analysis. It will determine the “date of Cut-off 2” when all patients entering the Extension part completed their assessment up to Week 48, or EOS visit following premature study drug discontinuation.

Table 2-11 Time at risk for AE and SAE: Cut-off 2 and final analysis

Category	Definition for Cut-off 2 analysis	Definition for final analysis
Time at risk for AE	Number of days in the study from first date of ofatumumab treatment to the earlier date of the following: - Safety cut-off - "Date of Cut-off 2"*	Number of days in the study from first date of ofatumumab treatment to safety cut-off.
Time at risk for SAE	Number of days in the study from first date of ofatumumab treatment to "date of Cut-off 2"*	Number of days in the study from first date of ofatumumab treatment to the last visit date, including Safety FU period.

*: "Date of Cut-off 2" is defined in section 2.1.1

Time-at-risk for AE and time at risk for SAE will be summarized in a similar way to exposure to investigational study medication.

Compliance to the study drug administration schedule will be calculated as duration of exposure to study drug in (days)/duration of on-treatment period in (days) * 100%. This rule means that compliance will be measured during the time interval the patient took study medication: premature discontinuation from study drug will not be considered non-compliance. Compliance to study drug administration will be summarized descriptively on SAF by treatment group. In addition, compliance will be summarized with cumulative number and percentage of patients in each compliance category (i.e., >= 20%, >= 30%, >= 40%, >= 50%, >= 60%, >= 70%, >= 80%, >= 90%, >= 95%, >= 98%, = 100%)

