COMD04	Leflunomide or teriflunomide while taking study treatment	Excluded from PPS
OTH01	EDSS rater acted as a treating physician or treating physician acted as EDSS rater	Excluded from PPS
OTH02	Not following per protocol blinding procedures such that the integrity of the study is compromised	Excluded from PPS

Table 5-5 Patient Classification

Analysis Set	PD ID that cause patients to be excluded	Non-PD criteria that cause patients to be excluded
FAS	INCL01 INCL01A	Not assigned a valid randomization number; Randomization despite screen failure
PPS	As listed in Table 5-4	Not in FAS; Compliance to study drug administration < 80% EDSS baseline value >=7.0
SAF	INCL01, INCL01A	No double-blind study drug taken

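### The compliance formula cannot see missed loading injections: a patient who misses Day 7 and Day 14 scores 100%, and no other per-protocol criterion picks this up

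*SAP*

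**What the plan says.** SAP 2.4.1 defines exposure as last dose date minus first dose date plus 31 days, less the excess over 31 days of every long gap. Long gaps "refer to consecutive injections with injection dates more than 31 days apart". The stated reason for 31 days is the monthly interval of 28 ± 3 days. The same section then says "Compliance to the study drug administration schedule will be calculated as duration of exposure to study drug in (days)/duration of on-treatment period", and adds that stopping early does not count as non-compliance.

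The denominator comes from SAP 2.1.1: "On-treatment period is defined as the one between the first date of study drug and 30 days after the last date of study drug". For the Cut-off 1 last dose date, the same section says "it refers to the date when the last dose of randomized treatment is administered up to Week 24 visit", which is Week 20 for a patient on schedule.

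SAP Table 5-5 uses the result as a PPS exclusion: "Compliance to study drug administration < 80" per cent. SAP 5.6 says that classification rests entirely on the criteria listed there.

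Protocol 5.2 gives eight Core injections: Days 1, 7 and 14, then Weeks 4, 8, 12, 16 and 20. Protocol 3.3 reports that, on modelling, "a single dose of ofatumumab 20 mg sc is insufficient to reduce B-cell levels to" the target of 8 cells/µL or fewer, and that three separate loading injections were required to reach it in more than 95% of patients. Protocol 9.3 says that exposure will take the intended dosing frequency into account.

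**The concern.** The 31-day allowance suits the monthly phase. In the loading phase the planned spacing is 6 to 7 days, and Day 1 to Week 4 is under 31 days, so leaving out both remaining loading injections costs nothing. The measure is presented as adherence to the administration schedule, yet it ignores the part of the schedule that the protocol singles out as necessary for target depletion.

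Two outputs are affected. The compliance table would show full adherence where a quarter of the Core injections were missed. The PPS could also retain a patient with fewer injections than one it excludes. The PPS repeat is the only sensitivity analysis of the primary endpoint now specified (SAP 2.5.4), since SAP section 4 removed time to first relapse from that role.

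**Working it through.** The plan gives no worked compliance figure, so the check applies the formula to the Core schedule, taken as Days 1, 7, 14, 28, 56, 84, 112 and 140.

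- Exposure = (last − first) + 31 − Σ(gap − 31), summed over gaps above 31 days.
- On-treatment days = (last − first) + 31, counting both end days.
- Compliance = exposure / on-treatment days.

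**Full adherence.** 140 − 1 + 31 = 170; no gap exceeds 31; 170/170 = 100%.

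**Days 7 and 14 missed.** The Day 1 to Day 28 gap is 27 days, so nothing is subtracted: 170/170 = 100%. This holds wherever Week 4 falls in its ±3-day window. If Week 4 is given on Day 35, the gap is 34 and the score is 167/170 = 98.2%. With the last dose on Day 140, the gap after Day 1 must reach 66 days before the score drops below 80% (170 − 35 = 135; 135/170 = 79.4%).

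**Other patterns**

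| Missed | Received | Days subtracted | Score | PPS |
|---|---|---|---|---|
| Days 7, 14, Week 4 | 5/8 | 55 − 31 = 24 | 146/170 = 85.9% | in |
| Days 7, 14 and one of Weeks 8, 12, 16 | 5/8 | 56 − 31 = 25 | 145/170 = 85.3% | in |
| Days 7, 14, Week 20 | 5/8 | 0 (last dose Day 112) | 142/142 = 100% | in |
| Weeks 8+12 or 12+16 | 6/8 | 84 − 31 = 53 | 117/170 = 68.8% | out |
| Weeks 8+16 | 6/8 | 25 + 25 = 50 | 120/170 = 70.6% | out |
| Weeks 4+8 | 6/8 | 70 − 31 = 39 | 131/170 = 77.1% | out |
| Weeks 4+12 or 4+16 | 6/8 | 11 + 25 = 36 | 134/170 = 78.8% | out |
| Weeks 8+20 or 12+20 | 6/8 | 25 | 117/142 = 82.4% | in |
| Weeks 4+20 | 6/8 | 42 − 31 = 11 | 131/142 = 92.3% | in |
| Weeks 16+20 | 6/8 | 0 (last dose Day 84) | 114/114 = 100% | in |

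**Extension.** A placebo-switch patient dosed at Week 24 and then every 4 weeks from Week 28 to Week 44, without Weeks 25 and 26, has gaps of 28 days: (308 − 168) + 31 = 171; 171/171 = 100% with 6 of 8 injections received.

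**Other PPS criteria.** Table 5-4 has no deviation for missed injections; TRT01 and TRT02 concern incorrect, damaged or expired drug. In Table 5-5 the 80% rule is the only adherence criterion.

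**Day counting.** If the denominator is counted without the first day (169), both the fully adherent patient and the one without Days 7 and 14 score 170/169 = 100.6%; they remain indistinguishable. SAP 2.1.1 also limits the on-treatment definition to efficacy analyses, although compliance is summarised on the safety set. That wording should be reconciled but does not change these figures.

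**The case against.** The strongest defence is that a time-based measure is deliberate. The PPS definition in both documents illustrates a major deviation by the share of study time spent non-compliant, and two loading injections cover little of that time. This has force: if the stretch from Day 7 to Day 28 (21 days) were subtracted in full, the score would be 149/170 = 87.6% and the patient would stay in the PPS. It does not justify a score of exactly 100%, however, nor does it meet the Protocol 9.3 commitment on intended dosing frequency. SAP section 4 lists no departure from that commitment.

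It can also be said that cases should be rare. Core injections through Week 20 are given at site (Protocol 5.5.4), compliance is checked at each visit by syringe count (Protocol 6.3), and non-compliance is a listed reason for discontinuation (Protocol 5.6.2). That stands, and it keeps the point small. None of these checks feeds Tables 5-4 or 5-5, though.

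A reader might infer that anyone missing two monthly doses is excluded, so that the rule always treats maintenance omissions more harshly. The formula does not support this. Of the ten pairs of monthly doses, six give 68.8–78.8% and are excluded; the four that include Week 20 give 82.4–100% and are kept, because the last dose date moves earlier and the SAP chooses not to penalise early stopping. A reader might also infer bias in favour of ofatumumab. Nothing in the documents shows it. On the protocol's own depletion rationale, keeping an under-loaded ofatumumab patient would more plausibly dilute the PPS effect, and a placebo patient has merely missed placebo.

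**Conclusion.** The point holds as a minor one. As written, the formula assigns 100% to a patient with 6 of 8 Core injections when the missing two are Days 7 and 14. It keeps in the PPS a patient with 5 of 8 (85.3–85.9%, or 100% if the third missed dose is Week 20), while excluding one with full loading and 6 of 8 when both missed doses lie in Weeks 4 to 16. The figures assume on-schedule dosing otherwise and inclusive day counting.

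The number of such patients is unknown, and no bias in the PPS estimate has been quantified. The superiority test is on the FAS and is not affected. The consequence is limited to the compliance summary at each cut-off and to PPS membership.

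**What to change.** In SAP 2.4.1, define compliance as injections received divided by injections scheduled from the first dose up to the patient's last dose, and apply the 80% rule in Table 5-5 to that ratio. Stopping the denominator at the last dose preserves the rule that early discontinuation is not non-compliance; a denominator running to Week 20 for everyone would contradict it. Report missed loading injections as a separate line (Days 7 and 14; Weeks 25 and 26 for placebo-switch patients). State whether the blinded placebo injections at Weeks 25 and 26 count for the continuous-ofatumumab group.

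With this definition, missing Days 7 and 14 gives 6/8 = 75.0%; adding one of Weeks 4 to 16 gives 5/8 = 62.5%; adding Week 20 instead gives 5/7 = 71.4%. Missing Weeks 16 and 20 remains 6/6 = 100%.

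The cost is a wording change and one derivation; complete injection dates are already mandatory (SAP 5.1.1). The downside is that PPS membership may shift slightly. For example, Day 7 plus Week 8 missed scores 145/170 = 85.3% now but would become 6/8 = 75.0% and be excluded. This SAP version postdates the Core analysis, so any change to the Core PPS should be labelled post hoc and shown beside the set as originally defined. The separate line on loading injections can be added without altering any analysis set.

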2.4.2 Prior, concomitant and post therapies

Analyses described in this section will be performed on the SAF for Cut-off 1 analysis, and on ESAF for Cut-off 2 analysis.

2.4.2.1 Concomitant medication

Records on the Prior and Concomitant Medication CRF page will be coded using the WHO drug dictionary. All medications will be classified as prior, concomitant, or post-study drug discontinuation medication as follows

- Prior medications are defined as drugs taken and stopped prior to first dose of study medication
- Concomitant medications are defined as drugs taken at least once between first dose and last dose of study medication (including those started prior to first dose and continued into the treatment period).
- Post-study drug discontinuation medications will be drugs started after the discontinuation of randomized study medication.

For Cut-off 2 analysis, medications will be also classified by whether they are taken prior to or on or after start of ofatumumab treatment.

Medications will be categorized into one (and only one) of above classes based on recorded or imputed start and end dates. When incomplete or missing, dates will be imputed according to Novartis standards (details in PDS).

Medications in each of these 3 categories will be summarized separately by treatment group, ATC code and preferred term. ATC level 1 and level 3 will be used.

Data collected from the Previous MS disease modifying treatment pages will not be included in this summary (See [Section 2.3.3](#)).

2.4.2.2 Surgical and medical procedures

Records on the surgical and medical procedures CRF page will be coded using the MedDRA dictionary. All procedures will be classified as prior, concomitant or post-study drug discontinuation procedure, in the same way as done for concomitant medications. Surgical and medical procedures in each of these 3 categories will be summarized separately by system organ class, preferred term and treatment group.

Imputation rules for start and end dates will follow the same rule as for the concomitant medications.

2.4.2.3 Injection related premedication

Injection related premedication will be identified by subcategory “Injection related premedication” in concomitant dataset. Injection related premedication will also be summarized separately for each injection as well as cumulatively for all injections by each cut-off.

For Day 1 injection summary, the injection related premedication with start date on the same day as the first injection date will be included and summarized for each of the three protocol specified types (type 1: steroids, type 2: antihistamines and type 3: acetaminophen) and for the combination of the specified types (type 1 + type 2 + type 3 and type 2 + type 3). The steroids (type 1) will be identified by category “Steroid”. The antihistamine (type 2) will be identified by ATC level 3 “antihistamines for systemic use”. The antipyretics/analgesics (type 3) will be identified by ATC level 3 “other analgesics and antipyretics” and “anti-inflammatory and anti-rheumatic products, non-steroids”. In summaries for each combination of types, the number and proportion of patients who took any combination of types of injection related premedication at specified injection will be provided.

Rest injection specified summaries or cumulative summaries will be reported similarly.

2.5 Analysis of the primary objective

2.5.1 Primary endpoint

The primary endpoint is the number of Gd enhanced T1 lesions per scan across 4 MRI scans at Week 12, 16, 20, and 24 during the core part.

2.5.2 Statistical hypothesis, model, and method of analysis

The null hypothesis is that there is no difference in the number of Gd-enhanced T1 lesions per scan between ofatumumab and placebo during the Core part (Cut-off 1 analysis). The alternative hypothesis is that there is a difference between the 2 treatment groups.

- Superiority of ofatumumab over placebo will be concluded if the mean number of Gd-enhanced T1 lesions per scan in patients treated with ofatumumab is lower compared with placebo and the observed p-value for the between-treatment comparison is less than the two-sided significance level of 0.05.

The null hypothesis will be tested on the FAS using a negative binomial regression model with log-link. Each patient's total number of Gd-enhanced T1 lesions during the Core part will be used as the response variable, and natural log of the number of MRI scans will serve as the offset variable to adjust for the different number of MRI scans between patients. The model will include treatment, region (Japan or other countries), and baseline number of Gd-enhanced T1 lesions (0 or ≥ 1) as factors.

The number of Gd-enhanced T1 lesions per scan will be estimated by treatment with 95% confidence interval. The between treatment effect will be calculated as rate-ratio (ofatumumab/placebo) with 95% confidence interval and p-value will be provided. In addition, the relative reduction in the number of Gd-enhanced T1 lesions per scan will be computed as one (1) minus the rate-ratio and expressed as a percentage.

The number of Gd-enhanced T1 lesions will be summarized descriptively by visit-window and treatment group.

Analyses on Gd-enhanced lesions will exclude MRI evaluation performed within 14 days after termination of systemic corticosteroids and/or adrenocorticotrophic hormone.

The above summary analyses will be repeated with additional data from the extension part at the Cut-off 2 analysis ([Section 2.14](#)).

